5.4 Treatment after discontinuation of trial product

When discontinuing trial products, either at the scheduled end of trial visit or if trial product is discontinued prematurely, the patient should be switched to a suitable marketed product at the discretion of the investigator.

5.5 Rationale for treatment

Dosing range and treatment regimens in this trial reflect the recommended dosing in prescribing information for turoctocog alfa approved by regulatory authorities in India and worldwide.

13 June 2017 | Novo Nordisk Protocol Date: Trial ID: NN7008-4304 Version: CONFIDENTIAL UTN:U1111-1179-5950 Status: EudraCT no.:2017-002281-46 Page:

Trial population 6

Number of patients 6.1

Number of patients planned to be screened: 70

Number of patients planned to start on trial product: 60

Number of patients planned to complete the trial: 50

6.2 Inclusion criteria

For an eligible patient, all inclusion criteria must be answered "yes".

1. Informed consent obtained before any trial-related activities. Trial-related activities are any procedures that are carried out as part of the trial, including activities to determine suitability for the trial.

Final

20 of 81

- 2. Male, age above or equal to 12 years at the time of signing informed consent.
- 3. Patients with the diagnosis of congenital moderate or severe Haemophilia A based on medical records. (FVIII \leq 5%).
- 4. Documented history of at least 150 EDs to FVIII containing products.

6.3 **Exclusion criteria**

For an eligible patient, all exclusion criteria must be answered "no".

- 1. Confirmed inhibitors to FVIII (≥ 0.6 BU) at screening as assessed by central laboratory.
- 2. History of FVIII inhibitors.
- 3. Known or suspected hypersensitivity to trial product(s) or related products.
- 4. Previous participation in this trial. Participation is defined as signed informed consent.
- 5. Participation in any clinical trial of an approved or non-approved investigational medicinal product within 1 month before screening (visit 1).
- 6. Any disorder, except for conditions associated with haemophilia A, which in the investigator's opinion might jeopardise patient's safety or compliance with the protocol.
- 7. Immunocompromised patients due to HIV infection (defined as viral load ≥400.000 copies/mL and/or CD4+ lymphocyte count ≤200/µL). HIV status and CD4+ lymphocyte count /viral load results may be obtained at screening or from available medical records; results must be not older than 6 months.
- 8. Known congenital or acquired coagulation disorders other than haemophilia A.
- 9. Mental incapacity, unwillingness to cooperate, or a language barrier precluding adequate understanding and cooperation.

| Protocol | Date: 13 June 2017 | Novo Nordisk | Version: 2.0 | Status: Final | EudraCT no.:2017-002281-46 | Page: 21 of 81 |

6.4 Withdrawal from trial

A patient may withdraw consent at will at any time either by the patient or by the patient's parent or the patient's legally acceptable representative. The patient's request to withdraw from the trial must always be respected. See section 8.1 for procedures to be performed for patients withdrawing consent.

6.5 Criteria for premature discontinuation of trial product

A patient must be prematurely discontinued from trial product if the following applies:

- 1. Included in the trial in violation of the inclusion and/or exclusion criteria.
- 2. Simultaneous participation in another clinical trial of an approved or non-approved investigational medicinal product.
- 3. High titer FVIII inhibitor (>5 BU), confirmed by central laboratory.
- 4. Planned or emergency major surgery.
- 5. Severe allergic or anaphylactic reaction to trial product.
- 6. Clinically relevant thromboembolic event which requires treatment with anticoagulants.
- 7. Lack of haemostatic effect of the trial product.
- 8. Use of other FVIII products
- 9. Use of FVIII containing products (blood components, PCC) for more than 5 EDs.

The subject may be prematurely discontinued from trial product at the discretion of the investigator due to a safety concern.

See section 8.1 for procedures to be performed for subjects discontinuing trial product prematurely.

6.6 Patient replacement

Patients who discontinue trial product prematurely will not be replaced.

6.7 Rationale for trial population

Patients with moderate or severe haemophilia A and a history of exposure to FVIII products are selected as the most suitable group for evaluation of immunogenicity in previously treated patients, which is one of the objectives of this trial. A history of inhibitors may be a risk factor for inhibitor development which could heighten the risk of inhibitor formation in the trial if not excluded. In order to avoid interference with immunogenicity assessment, only patients who are immunocompetent and without inhibitors to FVIII products are selected. These selection criteria are in accordance with the EMA guideline. ²¹

 Protocol
 Date:
 13 June 2017
 Novo Nordisk

 Trial ID: NN7008-4304
 Version:
 2.0

 UTN:U1111-1179-5950
 Status:
 Final

Page:

22 of 81

7 Milestones

EudraCT no.:2017-002281-46

Planned duration of recruitment period: First patient first visit until last patient first visit (FPFV – LPFV): 16 months

Planned FPFV: 28-Feb-2018

End of trial is defined as last patient last visit (LPLV):

• Planned LPLV of the trial: 28-Oct-2019

The screening and recruitment rate will be followed closely via the interactive web response system (IWRS) in order to estimate when to stop screening. All investigators will be notified immediately when the recruitment period ends, after which no further patients may be screened and the IWRS will be closed for further screening.

Trial registration:

Information of the trial will be disclosed at clinicaltrials.gov and novonordisk-trials.com. According to the Novo Nordisk Code of Conduct for Clinical Trial Disclosure²², it will also be disclosed according to other applicable requirements such as those of the International Committee of Medical Journal Editors (ICMJE)²³, the Food and Drug Administration Amendment Act (FDAAA)²⁴, European Commission Requirements²⁵⁻²⁷ and other relevant recommendations or regulations. If a patient requests to be included in the trial via the Novo Nordisk e-mail contact at these web sites, Novo Nordisk may disclose the investigator's contact details to the patient. As a result of increasing requirements for transparency, some countries require public disclosure of investigator names and their affiliations.

The Primary Completion Date (PCD) is the last assessment of the primary endpoint, and for this trial it is last treatment (8 weeks after Baseline visit), corresponding to end of trial visit, see section 2. If the last patient is withdrawn early the PCD is considered the date when the last patient would have completed the end of trial visit. The PCD determines the deadline for the results disclosure at Clinicaltrials.gov according to FDAAA.

Protocol Trial ID: NN7008-4304 UTN:U1111-1179-5950 EudraCT no.:2017-002281-46

CONFIDENTIAL

Date: Version: Status: Page:

13 June 2017 | Novo Nordisk Final 23 of 81

8 Methods and assessments

8.1 Visit procedures

The following sections describe the assessments and procedures. These are also included in the flow chart (see section 2). It is important to comply with the visit window stated in the flow chart, to ensure that the trial products do not expire while they are in the patient's possession (see section 2).

Informed consent procedures: The patient or parent/LAR will be provided with full written and verbal information about the trial prior to conduct of any trial-related procedures/activities at the information visit, in accordance with GCP^{\perp} and local requirements, see section 18.2. Informed consent must be obtained before any trial related activity. A separate informed consent must be obtained for genotype and future research, see section 18.3 and 18.4.

A child assent form may be provided to children (below the age of 18). The child assent can be performed on a separate day. The investigator should check the progressing maturation of the child and his ability to assent throughout the trial.

Treatment in general: Trial product injection can be performed at visit 2, 3 and unscheduled visits. A trial product injection at visit 2 must be performed at the trial site to assess if the patient or parent/LAR can handle the trial product injection. If assessed necessary, training sessions must be planned for and documented in the patient's medical records.

If injection of trial product is performed at site between scheduled visits, this must be recorded at an unscheduled visit

Screening failures: For screening failures the screening failure form in the electronic case report form (eCRF) must be completed with the reason for not continuing in the trial. Serious and nonserious adverse events from screening failures must be transcribed by the investigator into the eCRF. The following must be collected and documented:

- Date of visit
- Date of informed consent
- Violated Inclusion and exclusion criteria
- Screen failure reason
- Date patient left the trial
- Data relating to AE/SAEs if applicable
- Demography

Follow-up on serious adverse events (SAEs) must be carried out according to section 12.3. A screening failure session must be made in the IWRS and the case book must be signed in eCRF.

Re-screening is NOT allowed if the patient has failed one of the inclusion or exclusion criteria, this includes re-sampling if the patient has failed one of the inclusion or exclusion criteria related to laboratory parameters.

Protocol		Date:	13 June 2017	Novo Nordisk
Trial ID: NN7008-4304	CONFIDENTIAL	Version:	2.0	
UTN:U1111-1179-5950		Status:	Final	
EudraCT no :2017-002281-46		Page:	24 of 81	

Premature discontinuation of trial product: If a patient prematurely discontinues trial product, the investigator must withdraw the patient from trial and undertake procedures similar to those for end of trial visit as soon as possible.

If a patient prematurely discontinues trial product (see section $\underline{6.5}$), the patient should attend a follow-up visit in addition to the end of trial visit (see section $\underline{8.1.6}$).

The primary reason for premature discontinuation of trial product must be specified in the eCRF, and final drug accountability must be performed. A treatment discontinuation session must be made in the IWRS.

Withdrawal from trial: Withdrawal criteria must be evaluated at every visit after consent. If a patient withdraws consent, the investigator must aim to undertake procedures similar to those for end of trial visit as soon as possible (see section 8.1.6)

The end-of-trial form must be completed in the eCRF, and final drug accountability must be performed even if the patient is not able to come to the trial site. A treatment discontinuation session must be made in the IWRS. The case book must be signed.

Although a patient is not obliged to give his reason(s) for withdrawing consent, the investigator must make a reasonable effort to ascertain the reason(s), while fully respecting the patient's rights. Where the reasons are obtained, the primary reason for withdrawing consent must be specified in the end-of-trial form in the eCRF.

Data review: Review of diaries and laboratory reports etc. must be documented either on the documents or in the patient's medical record.

If clarification of entries or discrepancies in the diary is identified then the patient must be questioned and a conclusion made in the patient's medical record. Care must be taken not to bias the patient.

8.1.1 Visit 0 - Information visit

The purpose of the information visit is to inform the patient and/or parent/LAR about the trial. If the patient decides to participate, the patient or parent/LAR must give signed dated informed consent prior to any trial-related activities. All patients will be provided with a copy of the patient information and a copy of the signed and dated informed consent form, see section 18.2.

Informed consent for obtaining genotyping and biospecimen (blood sampling for future research) must also be collected, if the patient or parent/LAR agrees to this. The informed consent for genotyping can be obtained later in the trial and at the latest before sampling for genotyping.

A washout period for minimum of 72 hours for FVIII containing products is needed, when collecting FVIII activity and FVIII inhibitor laboratory samples at the next visit (visit 1). A washout period of trial product is necessary in order to ensure that there is no interference of the trial product with the assay, see Table 8–1. The purpose of these analyses is to determine whether or not the

Protocol		Date:	13 June 2017	Novo Nordisk
Trial ID: NN7008-4304	CONFIDENTIAL	Version:	2.0	
UTN:U1111-1179-5950		Status:	Final	
EudraCT no :2017-002281-46		Page:	25 of 81	

patient can continue in the trial according the inclusion and exclusion criteria (see section $\underline{6.2}$ and $\underline{6.3}$).

Table 8–1 Minimum requirements for washout periods

Laboratory test	Washout period
Visit 1 – FVIII activity level	72 hours
Inhibitor sampling	48 hours

In case a patient does not fulfil the requirements of a washout period (e.g. the patient has received treatment for a bleeding episode), the visit should be rescheduled. Beside the washout period, the patient should stay on his normal treatment regime between information visit and visit 2.

Key reminders:

- Informed consent must be obtained before any trial related activities starts
- Inform about the washout period
- Schedule next visit

8.1.2 Visit 1 - Screening

Visit 1 is characterised as the screening visit. The visit must be scheduled 1 week after the information visit with a window of ± 2 days.

At this visit, the patient's medical history must be recorded using the patient's current medical journal and the patient's current medical status will also be evaluated. Furthermore the patient will be preliminary evaluated for enrolment by examining the inclusion and exclusion criteria against the above information. The final evaluation for enrolment will be performed at the next visit evaluating the laboratory results taken at this visit. Furthermore an inhibitor test and a FVIII activity test will be performed so the patient must withhold FVIII containing products for 72 hours prior to this visit to ensure there is no interference of a FVIII product with the assay.

Each patient will be assigned a unique 6-digit subject number which will remain the same throughout the trial. It must be stated in the medical records that the patient is participating in the trial, including the patient number.

The investigator must keep a patient screening log, a subject identification code list and a patient enrolment log. Only patients who have signed the informed consent form should be included on the logs. The patient screening log and patient enrolment log may be combined in one log.

Patient will be provided with a card stating that they are participating in a trial and giving contact address(es) and telephone number(s) of relevant trial site staff. Patients should be instructed to return the card to the investigator at the last trial visit or to destroy the card after the last visit.

All assessment to be performed at this visit are listed in section 2

 Protocol
 Date:
 13 June 2017
 Novo Nordisk

 Trial ID: NN7008-4304
 Version:
 2.0
 2.0
 Status:
 Final
 Final
 Page:
 26 of 81
 27 of 81
 27 of 82
 28 of 81
 27 of 81
 28 o

Key reminders:

- Informed consent must be obtained before any trial related activities starts
- Ask for concomitant illness
- Ask for concomitant medications
- Screening session IWRS must be performed
 - In case of screening failure a screening failure session in IWRS must be performed and the case book must be signed off
- Check for 72 hours washout of FVIII containing products before FVIII activity test and inhibitor test
- Ask if the patient has experienced any AEs during his visit
- Trial card must be dispensed
- Schedule next visit

8.1.3 Visit 2 - Baseline

Visit 2 is characterised as the baseline visit. The visit must be scheduled 3 weeks after visit 1 with a window of ± 7 days. This is to allow sufficient time for the arrival of the laboratory reports as all results are necessary for evaluation of the inclusion and exclusion criteria. These results must be available before determining whether or not the patient can continue in the trial.

After the final evaluation of the inclusion and exclusion criteria, the investigator has to inject the trial product the first time: After the first dose of turoctocog alfa the patient's medical status must be assess.

The investigator must judge if the patient or parent/LAR capability of handling the trial product injection and plan for home treatment training at unscheduled visit if necessary.

The diary must be handed out to the patient or parent/LAR and training must be done. The investigator should train in how to record and change information in the diary and that the patient or parent/caregiver should record in the diary preferably within 24 hours after a bleeding episode has occurred or after the treatment has been injected to ensure as accurate information as possible.

Trial product for home treatment must be dispensed to the patient or parent/LAR until next visit.

All assessments to be performed at this visit are listed in section $\underline{2}$.

Key reminders:

- Ask if the patient has experienced any AEs since last visit
- Ask for any concomitant medications since last visit
- Training for home injection and hand out the Direction for Use
- Hand out the diary and train how to use it
- Dispensing session for the first dose and dispensing trial product until next visit must be performed in the IWRS
- Schedule next visit.

8.1.4 Visit 3 - Treatment

Visit 3, must be scheduled 4 weeks after visit 2 with a visit window of ± 3 days. The main reasons for these visits are to review the patient's diary and to dispense trial product.

The diary must be collected and reviewed by the investigator or delegated site staff (see section 8.6.2). The review will include the haemostatic efficacy for treatment of bleeding episodes and evaluate the severity rating. The review should be performed together with the patient or parent/LAR, see section 8.6.2.

The assessments to be performed at these visits are listed in section $\underline{2}$

Key reminders:

- Ask if the patient has experienced any AEs since last visit
- Ask for any concomitant medications since last visit
- Collect and review the diary
- Dispensing session for trial product until next visit must be performed in the IWRS
- Schedule next visit
- Remind the patient about the coming 48 hours washout period

8.1.5 Visit 4 - End of trial visit

For patients who withdraw from the trial, an end of trial visit must be performed as soon as possible. For patients completing the trial, the end of trial visit must be 8 weeks after visit 2 with a window of ± 3 days. The main reason for the visit is to collect samples analysing for FVIII inhibitors, see section 8.4.2. The patient must therefore withhold FVIII treatment for 48 hours prior to this visit to ensure there is no interference of a FVIII product with the assay.

The diary must be collected and reviewed by the investigator or delegated site staff (see section 8.6.2). The review will include the haemostatic efficacy for treatment of bleeding episodes and evaluate the severity rating. The review should be performed together with the patient or parent/LAR, see section 8.6.2. The assessments to be performed at this visit are listed in Section 2

| Protocol | Date: 13 June 2017 | Novo Nordisk | Urn: U1111-1179-5950 | CONFIDENTIAL | Page: 28 of 81 | CONFIDENTIAL | Page: 28 of 81 | CONFIDENTIAL | CONFI

Key reminders:

- Ask of the patient has experienced any AEs since last visit
- Ask for any concomitant medications since last visit
- Ensure 48 hours washout of trial product before the inhibitor test
- Collect sample for inhibitor test
- Collect and review the patient diary
- Completion or treatment discontinuation session must be performed in IWRS

8.1.6 Follow up visit

Patients withdrawn, after visit 2, due to inhibitors must attend a follow up visit in order to evaluate the patient's inhibitor status. This visit should be performed within 4 weeks after end of trial visit with a visit window of \pm 3 days.

Patients who have completed the trial must attend a follow up visit in order to assess any possible AEs. Patients, who have completed the trial, must attend 12 weeks after visit 2, with a window of ± 3 days.

The assessments to be performed at this visit are listed in section 2.

Key reminders:

• Ask if the patient has experiences any AEs since last visit

8.1.7 Unscheduled visit

An unscheduled visit can be performed after the visit 1 has been performed. The date and time of the unscheduled visit must be recorded in the eCRF.

Several reasons can be given for the necessity for the unscheduled visit. The main purpose could be to record information that is important and is not covered by the scheduled visits. This information can be (but not limited to) laboratory tests, dosing adjustments, lab samples to confirm a positive inhibitor test or trial drug administration at site. Please note AEs, withdrawal criteria and concomitant medication must be assessed at every unscheduled visit.

The assessments that can be performed at this visit are listed in section $\underline{2}$.

Key reminders:

- Ask if the patient has experienced any AEs since last visit
- Ask for any concomitant medications since last visit
- Check for 48 hours washout of trial product before a possible inhibitor test

8.2 Patient related information/assessments

8.2.1 Demography

Demography will be recorded at screening and consists of:

- Date of birth
- Sex
- Race
- Ethnicity

8.2.2 Concomitant illness and medical history other than haemophilia

A **concomitant illness** is any illness, other than haemophilia A, that is present at the start of the trial (i.e. at the first visit, visit 1) or found as a result of a screening procedure or other trial procedures performed before exposure to trial product.

Medical history is a medical event, other than haemophilia A, that the patient has experienced in the past. Historical bleeding episodes or similar haemophilia related medical history should not be recorded in medical history as this will be collected in another eCRF form called "Haemophilia treatment and bleeding episodes history".

The information collected for concomitant illness and medical history should include diagnosis, date of onset and date of resolution or continuing, as applicable.

Any change to a concomitant illness should be recorded during the trial. A clinically significant worsening of a concomitant illness must be reported as an AE.

It must be possible to verify the patient's medical history in source documents such as patient's medical record. If a patient is not from the investigators own practice; the investigator must make reasonable effort to obtain a copy of patient's medical record from relevant party e.g. primary physician. The investigator must document any attempt to obtain external medical information by noting the date(s) when information was requested and who has been contacted.

8.2.3 Concomitant medication

A **concomitant medication** is any medication for treatment or prevention of a disease, other than the trial products, which is taken during the trial, from visit 1 (screening visit) to end of trial visit.

Protocol	1	Date:	13 June 2017	Novo Nordisk
Trial ID: NN7008-4304	CONFIDENTIAL	Version:	2.0	
UTN:U1111-1179-5950		Status:	Final	
EudraCT no.:2017-002281-46		Page:	30 of 81	

Details of any concomitant medication must be recorded at the first visit. Changes in concomitant medication must be recorded at each visit as they occur.

The information collected for each concomitant medication includes trade name or generic name, indication, start date and stop date or continuing.

If a change is due to an AE, then this must be reported according to section 12. If the change influences the patient's eligibility to continue in the trial, the monitor must be informed.

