Criteria for premature discontinuation of trial product			X	X			X
Concomitant illness		X					
Concomitant medication		X	X	X	X		X
Haemophilia treatment and bleed history		X					
Medical history		X					
Details of Haemophilia		X					
Informed consent	X	X					
Informed assent	X^{b}	X^{b}					
Genotyping consent, optional		X ^c					
Biospecimen consent		X^{b}					
Demography		X					
Body measurements		X					
Height		X					
Body weight		X	X	X			Xb
EFFICACY							
Bleeding episodes			X^d	X ^d	X ^d		

Protocol Trial ID: NN7008-4304 UTN:U1111-1179-5950 EudraCT no.:2017-002281-46

CONFIDENTIAL

Date: Version: Status: Page:

3 June 2017 2.0 Final 11 of 81

13 June 2017 | Novo Nordisk

						1
Information visit	Screening	Baseline	Treatment	End of trial	Follow-up	Unscheduled Visit
0		_	2	4	-	
			_		_	
0	±2	±7	±3	±3	±3	
	X				X	X
		X	X			X
	X					
		Xe	Xe			Xe
		Xe	Xe			Xe
		Xf	Xf	Xf		X^{f}
	X			X		
	X^{g}					
	X			X		
	X^h					
	X^h					
	X ^c					
	Xi			Xi		X ^b
		X^{j}				X^{j}
		X	X			
	X	X	X	X		X ^b
		X	X	X		
			X	X		
		X	X^{b}			X ^b
	X					
		X	X	X		
	Information visit	0 1 -4 -3 0 ±2 X X X X X X X X X X X X X	0	0	0	0 1 2 3 4 5 -4 -3 0 4 8 12 ^a 0 ±2 ±7 ±3 ±3 ±3 X X X X X X X X X X X X X X X X X X X X X X X X X X X X X X X X X X X X X X X X X X X X X X X X X X X X X X X X X X X X X X X X X X X X X X X X X X X X X X X X X X X X X X X X X X X X X X X X X X X X X X X X X X X X X X X X X X X X X X X X X X X X X X X X X X X X X X X X X X X X X X X X X X X X X X X X X X X X X X X X X X X X X X X X X X X X X X X X X X X X X X X X X X X X X X X X X X X X X X X X X X X X X X X X X X X X X X X X X X X X X X X X X X X X X X X X X

Protocol		Date:	13 June 2017	Novo Nordisk
Trial ID: NN7008-4304	CONFIDENTIAL	Version:	2.0	
UTN:U1111-1179-5950	CONFIDENTIAL	Status:	Final	
EudraCT no.:2017-002281-46		Page:	12 of 81	

- X^a If patient has withdrawn the follow-up-visit must be performed 4 weeks after end of trial visit
- X^b If applicable
- X° Genotype consent is not mandatory at visit 1, but has to be collected before genotype is sampled, see section 8.5.3.1
- X^d Bleeding episodes and dosing information are recorded in the diary
- X^e If hypersensitivity reaction or technical complaints are identified, please ensure to complete the relevant form, see sections 12.1.5 and 12.1.6
- X^f If patient had any surgical interventions (minor surgery), please ensure to complete the surgery form, see section 8.4.5

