4.2.2 Secondary endpoints

- Frequency of adverse drug reactions (AR) and serious adverse reactions (SAR) reported until follow-up, 12 weeks after first treatment
- Successful haemostatic effect of turoctocog alfa in the treatment of bleeding episodes during 8 weeks of treatment
- Total annualised consumption of turoctocog alfa measured during the 8 weeks of treatment
- Frequency of allergic or infusion reactions related to the trial product reported until follow-up, 12 weeks after first treatment

 Protocol
 Date:
 13 June 2017
 Novo Nordisk

 Trial ID: NN7008-4304
 Version:
 2.0
 2.0

 UTN:U1111-1179-5950
 Status:
 Final

Page:

17 of 81

5 Trial design

EudraCT no.:2017-002281-46

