17.1 Sample size calculation

Sample size is based on Indian Health Authorities (HA) requirements. Indian HA has mandated Novo Nordisk to perform a trial with 50 patients (completers). Based on Hanley's formula $\frac{31}{2}$ "the rule-of-three" we know that with approximately 95% power we will observe at least one patient with FVIII inhibitor (≥ 0.6 BU) if the incidence rate is as low as 6%. The same holds for any other type of adverse events.

17.2 **Definition of analysis sets**

All main descriptions and analyses of efficacy will be based on the Full Analysis Set, as defined in ICH E9 Guidelines (Statistical Principles for Clinical Trials). ³² The Full Analysis Set includes all

Protocol		Date:	13 June 2017	Novo Nordisk
Trial ID: NN7008-4304	CONFIDENTIAL	Version:	2.0	
UTN:U1111-1179-5950		Status:	Final	
EudraCT no.:2017-002281-46		Page:	62 of 81	

dosed patients with data after dosing. Only in exceptional cases will patients be excluded from the full analysis set. The patients to be excluded and the reasons for their exclusion must be documented and signed by those responsible before database lock. Only in exceptional cases data points will be excluded from analysis based on the full analysis set. The observations to be excluded from such analysis and the reasons for their exclusion must be documented and signed by those responsible before database lock. The patients and observations excluded from analysis sets or any analyses, and the reason for this, will be described in the clinical trial report.

The Safety Analysis Set will be identical to the full analysis set. The analyses of the safety endpoints will be based on the Safety Analysis Set. The observation period for safety analysis will be the on-treatment period with a post treatment window until the follow-up visit to capture all treatment emergent events. The observation period is therefore from fist treatment with trial drug (visit 2) until the follow-up visit.

No formal Per-Protocol analysis is planned. However, the sensibility of the results with respect to single patient's data may be investigated by performing additional analyses on subsets of data.

Missing inhibitor test will not be counted as a positive result. This is based on the plausible assumption that in case of any clinical signs of inhibitor development inhibitor testing will be performed in practice, so missing test is unlikely to indicate positive inhibitor.

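### Safety events are counted to week 12, but concomitant medication recording stops at week 8, when patients should switch to another FVIII product

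*Combined protocol and SAP*

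**What the plan says.** - **Counting window.** Section 4.2.2 lists two secondary safety endpoints that run to week 12: "Frequency of adverse drug reactions (AR) and serious adverse reactions (SAR) reported until follow-up, 12 weeks after first treatment" and "Frequency of allergic or infusion reactions related to the trial product reported until follow-up, 12 weeks after first treatment". Section 17.2 sets the matching analysis window: "The observation period is therefore from fist treatment with trial drug (visit 2) until the follow-up visit".
- **Recording window.** Section 8.2.3 defines concomitant medication as medication other than trial product taken "from visit 1 (screening visit) to end of trial visit". Section 8.1.5 puts that visit 8 weeks after visit 2 for completers. In the flow chart (Table 2–1) the row "Concomitant medication" is marked at visits 1 to 4 and at unscheduled visits, and is blank at follow-up. The only key reminder for the follow-up visit in section 8.1.6 concerns AEs.
- **Change of product.** Under section 5.4, at the scheduled end of trial visit or on premature discontinuation, "the patient should be switched to a suitable marketed product at the discretion of the investigator".
- **Analysis.** Section 17.4.1.2 defines an AR by the investigator's causality rating (probable or possible). It also summarises all AEs and SAEs whatever their causality. Events before first dose or after follow-up are listed separately, but nothing separates events before and after the end of trial visit. The allergic and infusion reaction endpoint gets no summary or listing of its own.

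**The concern.** The change of FVIII product falls inside the period in which events are counted but at the very end of the period in which other medication is recorded. During treatment the protocol controls this exposure: use of other FVIII products is a criterion for premature discontinuation in section 6.5. After week 8 the same exposure is expected, yet no scheduled visit records it.

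The protocol's own background makes confounding plausible. Section 3.1.2 says that 98% of FVIII concentrate consumption in India in 2014 was plasma-derived, that lower-purity concentrates may cause allergic reactions, and that the available plasma-derived products carry a residual infection risk. A rash or fever in week 10 could follow a dose of the replacement product. If it is rated possibly related to turoctocog alfa, it enters the AR count. If it is rated unlikely, it is left out. In neither case can the sponsor or a reader check the rating against a record of what the patient had been given. The overall AE and SAE summaries include the event regardless.

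**Working it through.** **The plan's own figure.** The only sample size figure is in section 17.1: about 95% probability of seeing at least one event at 6% incidence with 50 completers, said to hold for other adverse events too. Check: 1 − 0.94^50 = 0.955, so it reproduces. The present point does not depend on it.

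**Inputs.** First dose at visit 2 (day 0); end of trial visit at 8 weeks (day 56) ± 3 days; follow-up at 12 weeks (day 84) ± 3 days (flow chart, sections 8.1.5 and 8.1.6). Planned completers 50, planned to start treatment 60 (section 6.1).

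**Share of the counting window after recording stops (completers).**

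Share = (follow-up day − end of trial day) / follow-up day

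| Case | End of trial day | Follow-up day | Gap (days) | Share |
|---|---|---|---|---|
| Nominal | 56 | 84 | 28 | 28/84 = 33.3% |
| Shortest | 59 | 81 | 22 | 22/81 = 27.2% |
| Longest | 53 | 87 | 34 | 34/87 = 39.1% |

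In patient-time this is 50 × 4 = 200 of 50 × 12 = 600 patient-weeks for 50 completers, or 240 of 720 if all 60 complete.

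**Early discontinuations.** The flow chart footnote puts follow-up 4 weeks after the end of trial visit for withdrawn patients, so their share depends on when they stop. As an illustration, if a patient stops and has the end of trial visit at week 4, the share is 4/(4 + 4) = 50%.

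**Does other text close the gap?**
- Section 8.2.3 also asks for changes to be recorded at every visit. Read alone, that could include visit 5, but the definition in the same section and the blank flow chart cell both end at visit 4.
- Section 8.1.7 requires concomitant medication to be assessed at every unscheduled visit. That helps only patients who have such a visit after week 8.
- A product begun at visit 4 can be entered there with a start date and marked as continuing. A product first taken later, a change of product, or a stop date before an event is not captured at any scheduled visit.

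**After the change.** The part of the window without scheduled recording falls from 28 of 84 days to 0. Sample size, power and confidence level are unaffected.

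**The case against.** The strongest reply is that causality, not the concomitant medication form, decides what counts as an AR. The investigator has discretion over the replacement product, so can know what was given, and can rate an event unlikely when another cause is more probable (section 12.1.1). Three further safeguards exist:

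- Hypersensitivity reactions, serious or not, need a specific event form (section 12.1.5). Its fields are not in the documents, so one cannot assume that it omits other products.
- Confirmed inhibitors and suspected transmission of infection are always SAEs (section 12.1.2). SAEs require a safety information form, which has a section for alternative aetiology (section 12.2).
- Inhibitor tests on suspicion or for confirmation take place at unscheduled visits, where concomitant medication is assessed (sections 8.4.2.1 and 8.1.7).

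All of this stands, and it rules out several stronger readings. A reader might infer that events after week 8 cannot be attributed at all; the causality rating and the extra forms contradict that. A reader might take the 33% as time on another FVIII product; section 3.1.1 says that on-demand treatment is the main regimen in India, so some completers may take few or no doses in those four weeks. A reader might turn one misattributed event into a shift in an upper confidence limit; section 17.3 specifies such a limit only for inhibitor incidence, and section 17.4.1.2 gives none for ARs or allergic reactions.

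The reply does not supply a systematic record. The safety information form is required only for SAEs, so non-serious events other than hypersensitivity reactions have neither additional form. Nor do these safeguards affect the AE and SAE summaries, which do not depend on causality.

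**Conclusion.** The mismatch is real and worth correcting. For a completer, 4 of the 12 weeks in which safety events are counted (33.3% of calendar time, 27.2% to 39.1% across the visit windows) follow the last scheduled record of concomitant medication. Events with onset in that period can be rated for causality, but the ratings cannot be checked systematically against what the patient received. The AE and SAE summaries mix time on turoctocog alfa with time after the planned switch.

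The consequence lies mainly with the secondary safety endpoints and the overall AE tables. A reader might extend it to the primary endpoint. The documents do not support that: the scheduled inhibitor sample is taken at visit 4, section 17.3 dates a confirmed inhibitor to the first of two positive tests, and confirmatory sampling happens at visits where concomitant medication is assessed.

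The size rests on two assumptions: that completers attend visits 4 and 5 within their windows, and that the recording rules are those in section 8.2.3 and the flow chart. The documents do not let one estimate how many events, if any, would be misclassified. This is an inexpensive improvement to data collection and reporting, not a flaw that undermines the trial.

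**What to change.** 1. Amend section 8.2.3 and the visit 5 column of the flow chart so that concomitant medication is recorded through the follow-up visit. At minimum this should cover any FVIII-containing product, with its name and start and stop dates. Add the matching reminder to section 8.1.6, and make the definition in section 8.2.3 agree with its own sentence on recording changes at every visit.
2. In section 17.4.1.2, present AEs, SAEs, ARs and SARs by onset: up to the end of trial visit, and after it to follow-up. For early discontinuations, split at the last dose of trial product.

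The first change extends an existing form to a visit that already takes place. The second uses onset dates, which the plan already relies on for its separate listing. The downside is slight extra data entry and one extra column in the AE tables. Treatment, visits, endpoints and sample size do not change.
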